5.3 Flowchart of the study cohort assembly

	Optum		Mar	ketScan
	Less Excluded Patients	Remaining Patients	Less Excluded Patients	Remaining Patients
All patients		75,524,500		191,990,035
Patients meeting the cohort entry criteria of moderate to high risk Acute Coronary Syndrome undergoing PCI procedure	-75219388	305,112	-191556394	433,641
Patients with sufficient enrollment period in the claims database	-41910	263,202	-120017	313,624
Patients with moderate to high risk Acute Coronary Syndrome	-144114	119,088	-165792	147,832
Patients initiating clopidogrel 75mg or prasugrel 10mg within 14 days of discharge of PCI hospitalization	-56497	62,591	-54511	93,321

Patients without history of hemorrhagic stroke	-349	62,242	-392	92,929
Patients without intracranial neoplasm, AV malformation, or aneurysm	-186	62,056	-202	92,727
Patients without ischemic stroke occurring 90 days prior to PCI hospitalization	-163	61,893	-255	92,472
Patients with sufficient claims enrollment after PCI hospital discharge	-483	61,410	-1191	91,281
Parent: Final cohort		61,410		91,281
Did not meet cohort entry criteria	-80	61,330	0	91,281
Excluded due to insufficient enrollment	0	61,330	0	91,281
Patients with no prior use of clopidogrel	-3135	58,195	-3653	87,628
Patients with no prior use of prasugrel	-535	57,660	-958	86,670
Patients without qualification in >1 exposure category	-18	57,642	-20	86,650
Patients age 18 years or older	-2	57,640	0	86,650
Patients without cardiogenic shock during PCI hospitalization	-1811	55,829	-2457	84,193
Patients without refractory ventricular arrhythmias	-5341	50,488	-7235	76,958
Patients without New York Heart Association Class IV congestive heart failure	-416	50,072	-265	76,693
Patients without active internal bleeding or history of bleeding diathesis	-3974	46,098	-3739	72,954
Patients without thrombocytopenia (platelet count of less than 100,000/mm3)	0	46,098	0	72,954
Patients without anemia (hemoglobin <10 g/DI)	-886	45,212	-2039	70,915
Patients without a claim for thienopyridine 5 days or less before PCI hospitalization	-1	45,211	-1	70,914
Patients without daily treatments with NSAIDs or COX-2 inhibitors	-394	44,817	-654	70,260
Patients without concomitant medical illness that is potentially associated with reduced survival	-687	44,130	-235	70,025
Patients without severe hepatic dysfunction	-1755	42,375	-2041	67,984
Patients without issues on poor treatment compliance including alcoholism, mental illness, or drug dependence	-2927	39,448	-1981	66,003

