Marketscan: https://bwh-dope.aetion.com/projects/details/990/results/46158/result/0

Date conducted: December 15, 2019

In order to complete the initial power analysis, the dummy outcome of a 90-day gap in database enrollment will be used. This outcome is used to ensure that no information on the comparative risks of the outcomes of interest are available at this stage. Complete a 1:1 PS-matched comparative analysis using this outcome. PS should include only 3 covariates: age, sex, and combined comorbidity index. Power calculations are based on the formulas from Chow et al. (2008).

In order to complete the initial power analysis, the dummy outcome of a 90-day gap in database enrollment will be used. This outcome is used to ensure that no information on the comparative risks of the outcomes of interest are available at this stage.

Effectiveness research with Real World Data to support FDA's regulatory decision making: Protocol Template

Complete a 1:1 PS-matched comparative analysis using this outcome. PS should include only 3 covariates: age, sex, and combined comorbidity index. Power calculations are based on the formulas from Chow et al. (2008).

Reviewed by PI:	[name]	Date reviewed:	12/16/19
Reviewed by FDA:	[name]	Date reviewed:	1/2/20
Reasons for stopping			
analysis (if required):			

9. Balance Assessment after PS matching

Aetion report links (Prasugrel vs. clopidogrel):

Optum: https://bwh-dope.aetion.com/projects/details/989/results/46940/result/0
Marketscan: https://bwh-dope.aetion.com/projects/details/990/results/46941/result/0

Date conducted: 01/05/2020

After review of initial feasibility and power analyses, complete creation of the remaining covariates (see Table 1 below for list of covariates). Again, using the dummy outcome of a 90-day gap in database enrollment, complete a 1:1 PS-matched analysis. The PS should include the complete list of covariates (excluding laboratory values, which are missing in some patients).

• Provide plot of PS distributions stratified by treatment group.

Note- Please refer to Appendix B.

Report covariate balance after matching.

Note- For Table 1, please refer to Appendix B.

• Report reasons for censoring by treatment group.

  		
Overall	Referent	Exposure

Effectiveness research with Real World Data to support FDA's regulatory decision making

Dummy Outcome	0 (0.00%)	0 (0.00%)	0 (0.00%)
Death	123 (0.28%)	70 (0.32%)	53 (0.24%)

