Generic Name	prasugrel
Sponsor	Eli Lilly
Year	2009
	Primary composite endpoint of death from
Measurable endpoint	cardiovascular causes, nonfatal myocardial
I Wicasarabic Chaponic	infarction, or nonfatal stroke. The key
	safety end point was major bleeding.
Exposure	Prasugrel
Comparator	Clopidogrel
	patients with moderate-to-high-risk acute
Population	coronary syndromes with scheduled
	percutaneous coronary intervention
Trial finding	HR = 0.81 (95% CI 0.73–0.90)
Notes	
No. of Patients	13,608
Non-inferiority margin	-
Assay Sens. Outcome	
Assay Sens. Endpoint (from trial)	
Finding for potential Assay Sens.	
Outcome from trial-	
Power	0.90 to detect 20% reduction in the relative
	risk
Blinding	Double-blinded

Statistical Method	
	for the prevention of thrombotic
Approval indication	cardiovascular complications in acute
	coronary syndromes

Mortality-Dependent on data source.

1. All-cause mortality / inpatient mortality Identified using the vital status file-

Medicare

Identified using the discharge status codes-

Optum-

- 20 = EXPIRED
- 21 = EXPIRED TO BE DEFINED AT STATE LEVEL
- 22 = EXPIRED TO BE DEFINED AT STATE LEVEL
- 23 = EXPIRED TO BE DEFINED AT STATE LEVEL
- 24 = EXPIRED TO BE DEFINED AT STATE LEVEL
- 25 = EXPIRED TO BE DEFINED AT STATE LEVEL
- 26 = EXPIRED TO BE DEFINED AT STATE LEVEL
- 27 = EXPIRED TO BE DEFINED AT STATE LEVEL
- 28 = EXPIRED TO BE DEFINED AT STATE LEVEL
- 29 = EXPIRED TO BE DEFINED AT STATE LEVEL
- 40 = EXPIRED AT HOME (HOSPICE)
- 41 = EXPIRED IN A MEDICAL FACILITY (HOSPICE)
- 42 = EXPIRED PLACE UNKNOWN (HOSPICE)

Truven-

- 20 Died
- 22 Died
- 23 Died
- 24 Died
- 25 Died
- 26 Died
- 27 Died
- 28 Died
- 29 Died
- 40 Other died status or Expired at home (Hospice claims only) (depends on year)
- 41 Other died status or Expired in medical facility (Hospice claims only) (depends on year)

- 42 Other died status or Expired place unknown (Hospice claims only) (depends on year)
- 21 Died or Disch./Transf. to court/law enforcement (depends on year)

2. CV mortality

Information on CV mortality through data linkage with the National Death Index (NDI) will be available for Medicare at a later date. We will conduct secondary analyses using CV mortality at that time.

Major bleeding co	Major bleeding control outcome: 1 inpatient (any position)		
Major bleeding exclusion criteria: 1 inpatient (any position) or 2 outpatient diagnosis (separated by 7-365 days)			

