Diabetic Foot; n (%)	59 (0.9%)	54 (0.8%)	0.01	103 (0.7%)	91 (0.6%)	0.01	162 (0.7%)	145 (0.7%)	0.00
Gangrene ; n (%)	6 (0.1%)	4 (0.1%)	0.00	5 (0.0%)	9 (0.1%)	-0.04	11 (0.1%)	13 (0.1%)	0.00
Lower extremity amputation; n (%)	16 (0.2%)	22 (0.3%)	-0.02	18 (0.1%)	23 (0.2%)	-0.03	34 (0.2%)	45 (0.2%)	0.00
Osteomyelitis; n (%)	17 (0.2%)	16 (0.2%)	0.00	36 (0.2%)	21 (0.1%)	0.03	53 (0.2%)	37 (0.2%)	0.00
Skin infections; n (%)	200 (2.9%)	239 (3.5%)	-0.03	402 (2.7%)	436 (2.9%)	-0.01	0,602 (2.7%)	0,675 (3.1%)	-0.02
Erectile dysfunction; n (%)	217 (3.2%)	238 (3.5%)	-0.02	334 (2.2%)	326 (2.2%)	0.00	0,551 (2.5%)	0,564 (2.6%)	-0.01
Diabetes with unspecified complication; n (%)	138 (2.0%)	147 (2.2%)	-0.01	245 (1.6%)	244 (1.6%)	0.00	0,383 (1.7%)	0,391 (1.8%)	-0.01
Diabetes mellitus without mention of complications; n (%)	2,146 (31.4%)	2,128 (31.1%)	0.01	3,904 (25.9%)	3,932 (26.0%)	0.00	6,050 (27.6%)	6,060 (27.6%)	0.00
Hypertension: 1 inpatient or 2 outpatient claims within 365 days; n (%)	4,975 (72.8%)	4,998 (73.1%)	-0.01	9,576 (63.4%)	9,586 (63.5%)	0.00	14,551 (66.3%)	14,584 (66.5%)	0.00
Hyperlipidemia ; n (%)	5,523 (80.8%)	5,550 (81.2%)	-0.01	9,909 (65.6%)	9,936 (65.8%)	0.00	15,432 (70.4%)	15,486 (70.6%)	0.00
Edema; n (%)	188 (2.8%)	182 (2.7%)	0.01	255 (1.7%)	260 (1.7%)	0.00	0,443 (2.0%)	0,442 (2.0%)	0.00
Renal Dysfunction (non-diabetic) ; n (%)	910 (13.3%)	933 (13.7%)	-0.01	1,193 (7.9%)	1,157 (7.7%)	0.01	2,103 (9.6%)	2,090 (9.5%)	0.00
Occurrence of acute renal disease ; n (%)	381 (5.6%)	403 (5.9%)	-0.01	474 (3.1%)	485 (3.2%)	-0.01	855 (3.9%)	888 (4.0%)	-0.01
Occurrence of chronic renal insufficiency; n (%)	523 (7.7%)	547 (8.0%)	-0.01	557 (3.7%)	553 (3.7%)	0.00	1,080 (4.9%)	1,100 (5.0%)	0.00
Chronic kidney disease ; n (%)	500 (7.3%)	524 (7.7%)	-0.02	533 (3.5%)	533 (3.5%)	0.00	1,033 (4.7%)	1,057 (4.8%)	0.00
,	, ,	,	-	,· ,	\· /		, , ,	, , , , , , ,	-0.01

Table 1: Prasugrel 10 mg vs Clopidogrel 75 mg

Occurrence of hypertensive	397 (5.8%)	411 (6.0%)	-0.01	391 (2.6%)	410 (2.7%)	-0.01	788 (3.6%)	821 (3.7%)	-0.01
nephropathy; n (%)		/					/	()	
Occurrence of miscellaneous renal	348 (5.1%)	358 (5.2%)	0.00	422 (2.8%)	412 (2.7%)	0.01	0,770 (3.5%)	0,770 (3.5%)	0.00
insufficiency; n (%)	624 (0.20()	F72 (0, 40()	0.00	040 (0 40()	005 (5.00()	0.04	4.550/7.40/\	4 460 (6 70()	0.00
Glaucoma or cataracts; n (%)	631 (9.2%)	573 (8.4%)	0.03	919 (6.1%)	896 (5.9%)	0.01	1,550 (7.1%)	1,469 (6.7%)	0.02

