median [IQR]	0.00 [0.00, 0.00]	0.00 [0.00, 0.00]	0.00	0.00 [0.00, 0.00]	0.00 [0.00, 0.00]	0.00	0.00 (0.01)	0.00 (0.01)	0.00
HAS-BLED Score (ICD-9 and ICD-10),									
180 days									
mean (sd)	3.41 (0.67)	3.42 (0.67)	-0.01	3.16 (0.49)	3.16 (0.50)	0.00	3.24 (0.55)	3.24 (0.56)	0.00
median [IQR]	3.00 [3.00, 4.00]	3.00 [3.00, 4.00]	0.00	3.00 [3.00, 3.00]	3.00 [3.00, 3.00]	0.00	3.00 (0.55)	3.00 (0.56)	0.00
Drug eluting stent; n (%)	3,921 (57.4%)	3,947 (57.7%)	-0.01	7,223 (47.8%)	7,159 (47.4%)	0.01	11,144 (50.8%)	11106 (50.6%)	0.00
Bare metal stent; n (%)	4,286 (62.7%)	4,285 (62.7%)	0.00	7,177 (47.5%)	7,200 (47.7%)	0.00	11,463 (52.3%)	11485 (52.4%)	0.00
Use of CYP inhibitors; n (%)	1,028 (15.0%)	1,027 (15.0%)	0.00	2,162 (14.3%)	2,184 (14.5%)	-0.01	3,190 (14.5%)	3211 (14.6%)	0.00
Use of CYP inducers; n (%)	27 (0.4%)	32 (0.5%)	-0.01	94 (0.6%)	83 (0.5%)	0.01	0,121 (0.6%)	115 (0.5%)	0.01
Commercial vs Medicare Advantage-									
Business Type Code - CORRECT ONE -									
TRUVEN									
Commercial; n (%)	4,740 (69.3%)	4,686 (68.6%)	0.02	2,090 (13.8%)	2,184 (14.5%)	-0.02	6,830 (31.1%)	6870 (31.3%)	0.00
Medicare Advantage; n (%)	2,095 (30.7%)	2,149 (31.4%)	-0.02	13,007 (86.2%)	12,913 (85.5%)	0.02	15,102 (68.9%)	15062 (68.7%)	0.00
Commercial vs Medicare Advantage-									
Business Type Code									
COM = COMMERCIAL; n (%)	4,740 (69.3%)	4,686 (68.6%)	0.02	-	-	#VALUE!	4,740 (69.3%)	4,686 (68.6%)	0.02
MCR = MEDICARE; n (%)	2,095 (30.7%)	2,149 (31.4%)	-0.02	-	-	#VALUE!	2,095 (30.7%)	2,149 (31.4%)	-0.02
MCD = MEDICAID; n (%)	0 (0.0%)	0 (0.0%)	#DIV/0!	-	-	#VALUE!	0 (0.0%)	0 (0.0%)	#DIV/0!
NONE = NO BUSINESS LINE CODE	0 (0.0%)	0 (0.0%)	#DIV/0!	-	-	#VALUE!	0 (0.0%)	0 (0.0%)	#DIV/0!
(added in 2015); n (%)									
UNK = UNKNOWN (added in 2015); n	0 (0.0%)	0 (0.0%)	#DIV/0!	-	-	#VALUE!	0 (0.0%)	0 (0.0%)	#DIV/0!
(%)									
Commercial vs Medicare Advantage-									
Data Type									
1 - Fee For Service; n (%)	-	-	#VALUE!	11,534 (76.4%)	11,465 (75.9%)	0.01	11,534 (76.4%)	11,465 (75.9%)	0.01
2 - Encounter; n (%)	-	-	#VALUE!	1,473 (9.8%)	1,448 (9.6%)	0.01	1,473 (9.8%)	1,448 (9.6%)	0.01
3 - Medicare; n (%)	-	-	#VALUE!	1,821 (12.1%)	1,920 (12.7%)	-0.02	1,821 (12.1%)	1,920 (12.7%)	-0.02
4 - Medicare Encounter; n (%)	-	-	#VALUE!	269 (1.8%)	264 (1.7%)	0.01	269 (1.8%)	264 (1.7%)	0.01
Metropolitan Statistical Area - Urban									
(any MSA) vs Rural (non-MSA)									
Urban; n (%)	-	-	#VALUE!	11,804 (78.2%)	11,827 (78.3%)	0.00	11,804 (78.2%)	11,827 (78.3%)	0.00

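### Matched HAS-BLED balance is not evidence of balance on bleeding history, and no non-laboratory covariate demonstrably captures the prior bleeding and anaemia that pass the exclusions

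*Combined protocol and SAP*

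**What the plan says.** Section 9 says of the PS: "The PS should include the complete list of covariates (excluding laboratory values, which are missing in some patients"). Table 1 in Appendix B is that list. Its HAS-BLED row, labelled "HAS-BLED Score (ICD-9 and ICD-10"), gives only the coding systems and a 180-day window, with no items, weights or codes.

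After matching, the row reads mean 3.16 (SD 0.49) for clopidogrel and 3.16 (0.50) for prasugrel in MarketScan (headed Truven), with median and quartiles "3.00 [3.00, 3.00"] in both arms. In Optum it reads 3.41 (0.67) and 3.42 (0.67), quartiles 3 to 4. The matched standardised differences are 0.00 and -0.01. Before matching they were 0.38 in MarketScan and 0.45 in Optum, with clopidogrel higher.

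Bleeding history is also handled by restriction. The Section 5.3 flowchart line "Patients without active internal bleeding or history of bleeding diathesis" removes 3,974 Optum and 3,739 MarketScan patients. Appendix A assesses this over the 180 days before drug initiation, and its code sheet requires "1 inpatient (any position) or 2 outpatient diagnosis (separated by 7-365 days"). Anaemia (exclusion 11) removes 886 and 2,039 patients. It is read only from inpatient codes during the index hospitalization.

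**The concern.** A reader of Table 1 will take the matched HAS-BLED difference as showing that the arms are alike on bleeding risk, including past bleeding. That holds only if past bleeding moves the score. The printed level is well above what the tabulated components suggest, and the pattern across columns is explained almost wholly by other rows of the same table.

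This matters because the exclusions leave a gap. A patient with one outpatient bleeding code stays in, and so does a patient whose anaemia was coded only before the index stay. Outside the laboratory rows, Table 1 has no row for either. If such histories influenced the choice of drug, they could stay unbalanced without Table 1 showing it. Major bleeding is the positive control by which Section 6.3.1 judges validity, so it is the outcome most exposed.

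**Working it through.** **Inputs.** All counts come from Table 1. Assumption: the items are those the acronym names (hypertension, renal, liver, stroke, bleeding, labile INR, age 65 or over, drugs, alcohol), at one point each.

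**1. The table's own arithmetic reproduces.** Standardised difference = (m1 - m2) / sqrt((s1² + s2²)/2).
- Unmatched MarketScan: (3.38 - 3.16) / sqrt((0.65² + 0.50²)/2) = 0.379, printed 0.38.
- Unmatched Optum: (3.74 - 3.42) / sqrt((0.76² + 0.67²)/2) = 0.447, printed 0.45.

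**2. Level.** The mean of a sum of 0/1 items equals the sum of their prevalences, whatever their correlation. Give every patient one drug point for the study antiplatelet, count every oral anticoagulant user as labile INR, and leave out bleeding.
- Matched MarketScan prasugrel (n = 15,097): 1 + (9,586 hypertension + 2,144 age + 1,157 renal dysfunction + 390 stroke + 169 alcohol + 5 liver + 393 anticoagulant)/15,097 = 1.92. Printed 3.16, gap 1.24.
- Matched Optum prasugrel (n = 6,835): 1 + (4,998 + 2,230 + 933 + 287 + 0 + 2 + 171)/6,835 = 2.26. Printed 3.42, gap 1.16.
- The clopidogrel arms give 1.91 (gap 1.25) and 2.24 (gap 1.17).

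More generous scoring does not close the gap. In matched MarketScan prasugrel, NSAID use as an extra point (1,952/15,097 = 0.129) and hypertension set to 100% (adding 0.365) give 2.41, still 0.75 short.

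**3. Quartile.** Give everyone both the drug and the hypertension point. A score of 3 then needs one more item. Without bleeding, at most 0.142 + 0.077 + 0.026 + 0.011 = 0.256 of matched MarketScan prasugrel patients can have one, under any correlation. Adding all anticoagulant users gives 0.282; adding NSAIDs as a separate point gives 0.411. A lower quartile of 3 implies about 0.75. A bleeding item would have to fill the rest: 0.75 - 0.411 = 0.34 up to 0.75 - 0.256 = 0.49 of a cohort from which bleeding was excluded.

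**4. Pattern across columns.** The last column is the printed mean minus the three shares before it, calculated from unrounded counts.

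| Column | Mean | Hypertension | Age ≥65 | Chronic renal insufficiency | Any stroke | Remainder |
|---|---|---|---|---|---|---|
| Optum unmatched, clopidogrel | 3.74 | 79.9% | 55.8% | 14.5% | 7.4% | 2.963 |
| Optum unmatched, prasugrel | 3.42 | 73.2% | 32.5% | 8.0% | 4.2% | 2.974 |
| MarketScan unmatched, clopidogrel | 3.38 | 66.5% | 31.1% | 6.4% | 4.9% | 2.957 |
| MarketScan unmatched, prasugrel | 3.16 | 63.5% | 14.1% | 3.7% | 2.6% | 2.956 |
| Optum matched, clopidogrel | 3.41 | 72.8% | 31.0% | 7.7% | 4.4% | 2.980 |
| Optum matched, prasugrel | 3.42 | 73.1% | 32.6% | 8.0% | 4.2% | 2.972 |
| MarketScan matched, clopidogrel | 3.16 | 63.4% | 13.7% | 3.7% | 2.4% | 2.962 |
| MarketScan matched, prasugrel | 3.16 | 63.5% | 14.2% | 3.7% | 2.6% | 2.956 |

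The remainder spans 0.024 while hypertension spans 0.165. With the renal dysfunction row instead, plus alcohol and liver, the remainder is 2.895 to 2.923, equally flat.

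**5. Spread.** With independent items, the SD from age, renal dysfunction, stroke, alcohol and liver is 0.48 in matched MarketScan, against 0.49 to 0.50 printed. Letting hypertension vary at its tabulated 63% would give 0.68.

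**6. Share at exactly 3, matched MarketScan.** P(score ≠ 3) is at most SD² + (mean - 3)² = 0.25 + 0.0256 = 0.28 for prasugrel. A linear programme over scores 0 to 9, using the printed mean, SD and quartiles with rounding, puts 72% to 91% at exactly 3.

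**7. Possible size of bias (assumed inputs, and assuming the matched covariates do not already absorb the difference).** Sub-threshold prior bleeding in 6% of clopidogrel and 4% of prasugrel patients, relative hazard 2, multiplies the bleeding HR by 1.04/1.06 = 0.98. With 10% against 5% and relative hazard 3, the factor is 1.10/1.20 = 0.92. Both would understate excess bleeding on prasugrel.

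**The case against.** The item list is an assumption. The documents print none and refer readers to an external folder for details. The table's hypertension row ("Hypertension: 1 inpatient or 2 outpatient claims within 365 days; n") also mentions a 365-day span, while the score uses 180 days. A reader might infer that the printed row is impossible. The documents do not support that: they show an unexplained offset, not a contradiction, and a bleeding item is left out of the bound only because bleeding is an exclusion.

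The fit in step 4 is approximate. The chronic renal insufficiency row was chosen because it fits; with renal dysfunction in the same three-item sum, 3 plus the shares exceeds the printed means by about 0.08 to 0.10. If independent, the three variables give SD 0.43 in matched MarketScan prasugrel and 0.58 in matched Optum prasugrel, against 0.50 and 0.67. Correlation or other items must supply the difference, so it is not shown that the row repeats those three variables and nothing else.

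A constant offset is absorbed by the PS intercept and does no harm. The exclusion is broad; its code list includes epistaxis and microscopic haematuria. Related rows exist and are balanced: anticoagulants, NSAIDs, faecal occult blood tests and PT/aPTT tests. Haemorrhagic stroke is tabulated too, but its history is an exclusion, so it carries almost nothing. Haemoglobin is a laboratory value outside the PS. In Optum its standardised difference still falls from -0.35 to -0.04 after matching. That is reassuring but partial: 86.5% of matched Optum patients have no value, and over 99% in MarketScan.

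All of this limits the size of the problem. None of it shows that sub-threshold bleeding or earlier anaemia is measured in the PS.

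**Conclusion.** The point stands in a limited form. On the acronym's item list, the matched HAS-BLED means are about 1.2 points above the sum of the tabulated items. They track age, renal disease and stroke, with no visible hypertension contribution. The near-zero matched difference is therefore not evidence of balance on bleeding history. No non-laboratory covariate demonstrably captures a single outpatient bleeding code, or anaemia coded only before the index stay.

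Three stronger readings should be resisted. Not almost every matched MarketScan patient sits at 3: 9% to 28% do not, and Optum is wider. The PS is not without any working measure of bleeding risk: the score varies, separates the arms before matching and is balanced afterwards. No effect on the primary MACE analysis is shown.

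Residual bias is probably small, 2% to 8% in the illustrations, whose inputs are assumed. It bears mainly on the major-bleeding control, which Section 6.3.1 uses only to judge validity. The change is cheap, and Section 13 carries no run date.

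**What to change.** Before Section 13 is run:

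1. Add two binary PS covariates from the code lists already in Appendix A, both measured before the index admission: any bleeding code that does not meet the exclusion, and anaemia. Refit the PS, re-match in each database, and update Table 1 and the matched counts in Section 10.
2. Check the HAS-BLED construction item by item, with each item's definition and prevalence by arm. If its items score features that every patient in this cohort has, correct the score or drop it from the PS.

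The cost is two flags from existing lists, a check of one covariate, and one re-match per database. The matched number may fall slightly. It is now 6,835 of 6,872 prasugrel patients in Optum (99.5%) and 15,097 of 15,187 in MarketScan (99.4%), so there is room.
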